Regarding aim 3, we will use the VQ-VAE model trained on all of the movie data, and only train the SAB component of the recurrent DNN to solve each particular task. We will evaluate the performance of this variant of the model using ten-fold cross-validation (within each task) and expect this variant of the recurrent DNN to be easier to train and outperform the DNNs trained specifically on each task, as described in aim 2. This analysis will test directly that the representation learned on movies, or video games transfer well to other cognitive context (language, memory, image).

Sample size

The primary aim of this project is to demonstrate our ability to efficiently train artificial DNNs to solve a variety of task. Potentially this could be achieved with data collected on a single human participant. The limiting factor is here the amount of data available on each individual. The amount of individual data will exceed what was collected in the only comparable study we are aware of (Fong et al., 2018). We do not think we can realistically collect more data than currently planned, because of the large time demands already required from the research participants. To check that our observation generalize we would like to have three participants for each task, which we increased to four to anticipate participants potentially dropping out of the study. Because we will be testing three tasks in parallel, the core cohort will therefore include 12 subjects.

¹⁷ <https://fmripipeline.readthedocs.io/en/stable/citing.html>

¹⁸ https://neuropicon.github.io/neuropicon_doc/

¹⁹ <http://visbrain.org/>

²⁰ <https://etiennecmb.github.io/brainpipe/>

²¹ <https://etiennecmb.github.io/tensorpac/>

References

- Boot, W.,R., Kramer, A., F., Simons, D., J., Fabiani, M., & Gratton G., 2008. The effects of video game playing on attention, memory, and executive control. *Acta Psychologica*, 129, 387–398.

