Overview of the project. In this project, we are planning to scan extensively a handful of participants in a variety of cognitive tasks. The scanning will occur weekly in functional MRI over a year (roughly 50 scanning sessions), and bi-weekly in MEG (roughly 10 scanning sessions). The fMRI and MEG techniques were selected because of their complementary insights into brain function: good spatial resolution for fMRI, excellent temporal resolution for MEG. The core of each session will consist of watching a series of videos, composed of short clips selected to cover a variety of actions, as well as longer movies featuring more extensive narrative. These data will let us develop and validate a new class of DNNs able to capture brain dynamics efficiently, while scaling to large numbers of parameters (Aim 1). Each subject will also perform tasks drawn from, or inspired by, recent AI research. These tasks cover the memory, vision and language domains. By collecting extensive task battery on the same subjects as well as movie, we will be able to test if the DNNs trained on the movie data have extracted features that can be used to achieve good performance on a variety of tasks (Aim 2). We will also be able to test if training on one of the task will increase the speed of learning on the other tasks as well (Aim 3).

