As part of the main project, we will recruit about 12 participants, over the age of 18 to join the study for a minimum of five years. Participants will be recruited by word of mouth, as we hope to find participants that will be able to commit to the extensive time commitment required by the study, and that are likely to remain throughout the course of the project. Exclusion criteria include visual or auditory problems that would prevent participants from seeing and/or hearing stimuli in the scanner, chronic or recent (i.e. in the last two years), psychiatric or neurological problems. In addition, the standard exclusion criteria for MRI and MEG will apply.

In addition, we will recruit 6 participants, to act as a control group for the *auditory battery* (see section below). These participants will be tested on the *auditory battery* at the same frequency as original 12, only they will not undergo scanning. The goal of these controls is to account for any potential changes in auditory performance related to learning or practice, particularly on the *MATRIX test* (see below), where the same stimuli will be repeated at each session.

Auditory sessions

There will be two types of auditory sessions; *auditory battery*, and the *auditory attenuation pilot*.

The **auditory battery** is designed to ensure that we can monitor, and quantify any temporary, and/or permanent change in participants' auditory systems as a result of repeated exposure to different types of scanning related noise. The auditory battery will be done approximately once a month, or every four scans, and will last around 60 minutes. All hearing tests will be carried out in a soundproof booth and will be administered by trained staff. All tests are non-invasive, and carry no risk to the participants.

Hearing tests included in our battery:

Pure-tone Audiometry (20 min): This test measures hearing acuity for tones at low to high frequencies (Hz), and at different intensities (dB), (Huizing, 1951). Participants will be asked to wear a set of headphones and instructed to raise their hand when a sound is detected. For every correct answer the volume will be lowered, and for every incorrect answer the volume is increased. This process is repeated until a participant responds to a test signal (or tone), 70% of the time on ascending trials (i.e. when we establish their threshold). Thresholds will be measured for a range of both low, and high frequencies (500-1600 Hz).

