The **sound attenuation pilot** (60 minutes), will be used to quantify the efficiency of MRI compatible ear muffs we built at UNF. Each participant will have their free-field thresholds tested in the following conditions: 1) with nothing, to establish their baseline, 2) with the sensimetrics earbuds (MR-compatible sound delivery system available at UNF that provides about 20 dB of sound protection at higher frequency⁵), 3) with earbuds and headcase (see Personalized headcase section), 4) with earbuds, headcase and earmuffs. During the assessment, the participants will sit in a soundproof booth, facing two speakers, located on either side of their chair, at an approximately 45 degree angle. Sounds will be presented to the participants via the two speakers, and participants will be instructed to press a button every time they hear a sound. Similarly to the Pure-tone audiometry (see above), free-field thresholds measure hearing acuity for tones at low to high frequencies (Hz), and at different intensities (dB), only sounds are presented via the speakers instead of headphones.

Personalized headcases

In order to minimize movement during neuroimaging scans, for each participant we will purchase a custom-designed, personalized headcases from Caseforge⁶. In order to personalize the headcases, we will need to scan each participant's head using a handheld 3D scanner. The images will be sent to Caseforge's secure servers where they will be used to mill two personalized headcases for use in the MRI, and MEG scanners.

The **motion task** (60 minutes), the goal of this task is to quantify the amount of head motion with and without the personalized headcase. Small Qr codes, called ArUco⁷, will be placed on the participants' head, and motion will be recorded using an MRI compatible camera. Participants will be scanned in both the fmri and MEG, with and without their headcases, doing a variety of tasks. These tasks will include watching resting state, reading a text out loud, watching a video, and playing a video game.

Autonomic measures

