Participants will attend a recruitment session where they be given the consent form to read over. The exclusion criteria, and MRI & MEG screening criteria will also be checked. Upon acceptance of participants, the screening questionnaire, will be given to the subject, and a three-dimensional image of their head will be acquired using a Caseforge hand-held scanner. Future scanning and testing session will be scheduled for the upcoming month.

Structural MRI sessions (60 minutes) will be acquired approximately once every 3 months. The purpose of these session is to collect various types of structural information. Using the 64-channel head coil and standard UNF sequences, we will acquired the following types of scans: T1 ME-MPRAGE (9 min), Diffusion-weighted scan (6 min), MTstat (6 min), MP2RAGE (5 min), T2 -SPACE (6 min), PD-weighted images (10 min). During the scans participants will be instructed to relax, and try to remain still.

fMRI sessions (60 minutes). Images will be acquired on the 64-channel head coil using a MB sequence developed at l'UNF. Participants will be asked to participate in two type of tasks that will last about 30 minutes; during the video task they will watch videos of vary lengths, and the video game task (see below). The other task will be one of the following:

The **language task** (13 minutes). Participants will be presented word triplets; one target word, followed by two words shown side by side. Participants will be instructed to selected which of the two words are most similar to the target word. They will use an MR-compatible mouse to record their choice (a - left words; - right word). Stimuli will be presented using a randomized inter-stimulus interval, and during the interstimulus interval participants will be presented a blank screen.

The **reading task** (15 minutes). During this task, 10 participants will be asked to read out loud a text that they see on the screen. This task will be used to quantify motion and to assess the efficacy of the headcase at reducing motion.

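### Pure-tone audiometry is fixed at 500-1600 Hz, which contradicts the protocol's own description of low and high frequencies, and no hearing battery is placed before the first scan

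*Protocol*

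**What the plan says.** Under Auditory sessions, the protocol gives the battery its purpose: to "monitor, and quantify any temporary, and/or permanent change in participants' auditory systems as a result of repeated exposure" to scanning noise. It has four tests: pure-tone audiometry, tympanometry, otoacoustic emissions (OAE) and the MATRIX speech-in-noise test. Only the audiometry has a frequency range: "Thresholds will be measured for a range of both low, and high frequencies (500-1600 Hz".

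The timing rule is "The auditory battery will be done approximately once a month, or every four scans, and will last around 60 minutes". The 12 scanned participants and 6 unscanned controls are tested at the same frequency. The controls are there to account for learning or practice.

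Under Experimental Procedures, the recruitment session covers the consent form, exclusion criteria, MRI and MEG screening, a questionnaire and a three-dimensional head image. No hearing test is listed. The text then says "Future scanning and testing session will be scheduled for the upcoming month", without saying whether a scan or a test comes first.

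The sound attenuation pilot compares free-field thresholds with and without protection. It describes its measurement as similar to the pure-tone audiometry but gives no range. It says that the earbuds' sound delivery system "provides about 20 dB of sound protection at higher frequency".

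**The concern.** The audiometry sentence promises low and high frequencies and then gives an upper limit of 1600 Hz. Staff who follow the number would measure nothing above 1.6 kHz. Pure-tone audiometry is the only test in the battery that yields a hearing threshold by frequency, so its range largely decides which changes can be located and quantified. If noise damage tends to appear first above about 2-3 kHz (an assumption from general audiology, not in the protocol), the stated range lies wholly below the region of most interest.

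The second matter is the reference point. Change due to exposure is best measured from an unexposed value in the same person. The protocol gives how often the battery recurs but not when it starts, nor how long after a scan it takes place. A first audiogram taken after several scans has already absorbed any early effect, and that pre-exposure value cannot be recovered later. An unrecorded scan-to-test lag makes it harder to tell a transient shift from a lasting one, which is the distinction the battery is meant to draw.

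**Working it through.** **Inputs from the protocol.** Audiometric range 500-1600 Hz; battery about monthly or every four scans; "The scanning will occur weekly in functional MRI over a year (roughly 50 scanning sessions"); fMRI sessions of 60 minutes; participation for at least five years.

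**1. The plan's own interval, reproduced.** Counting fMRI sessions only:
- Scans per month: 50/12 = 4.17, against the stated four.
- Batteries per year at one per four scans: 50/4 = 12.5, against 12 at one per month.

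The two forms of the schedule agree, so the interval is not in error.

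**2. Frequency span.** Octaves = log2(upper/lower).
- As written: log2(1600/500) = 1.68 octaves.

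The protocol does not give another upper limit, so a range of assumed values is shown:

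| Assumed upper limit | Octaves from 500 Hz | Share covered by 500-1600 Hz |
|---|---|---|
| 4000 Hz | 3.0 | 1.68/3.0 = 56% |
| 8000 Hz | 4.0 | 1.68/4.0 = 42% |
| 16000 Hz (one dropped zero) | 5.0 | 1.68/5.0 = 34% |

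Under any of these limits, between 44% and 66% of the span in octaves would go untested.

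**3. Whether the other tests fill the gap.** Tympanometry assesses the middle ear. The OAE section gives no frequency range and describes emissions as absent once loss exceeds 25-30 dB, so as described it does not quantify smaller shifts. MATRIX scores sentence understanding in noise, and the protocol itself expects possible practice effects there because the stimuli repeat. These tests add information on hearing, but none is described as giving thresholds by frequency.

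**4. Exposure before the first measurement.** If the first battery follows the fourth scan, 4 x 60 min = 4 hours of fMRI come first. If it precedes the first scan, none does. The text allows both.

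**5. Scan-to-test lag.** With weekly scans and no rule, the time from the last scan to a battery can be anything from 0 to about 7 days.

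**6. Total exposure being monitored.** About 50 sessions a year x 5 years = 250 sessions, if the first-year rate holds (an assumption; the protocol states the weekly rate for one year).

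**The case against.** The strongest reply is that 1600 is a slip. The protocol speaks of low to high frequencies in both the audiometry and the attenuation pilot, so the intent is consistent, and the remedy is one number rather than a redesign. That is fair, and a dropped zero is plausible. But the figure is the operative instruction and no other passage corrects it.

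Several stronger readings are tempting, and the protocol does not support them:

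- A reader might infer that the whole battery is confined to 500-1600 Hz. It is not; the figure belongs to the audiometry alone, and OAE in particular probes the inner ear without that stated limit.
- A reader might infer that the attenuation pilot is confined to the same range, so that protection is judged outside the region where it is claimed. The pilot says only that its measurement is similar and names no range. It is unspecified, not wrong.
- A reader might infer that there will be no pre-exposure measurement. This rests on silence: the schedule gives an interval without a start date, and nothing rules out a first battery before the first scan. The bare-ear baseline in the pilot does not settle it, since it is not part of the battery and is not placed before scanning.
- A reader might infer that temporary and permanent shifts cannot be told apart. Roughly 12 batteries a year offer partial separation: a lasting shift should recur, while a transient one should fluctuate if lags vary. What is missing is the recorded lag that would make this comparison interpretable.

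It is also true that the three aims and the sample-size rationale concern neural networks, so the scientific conclusions do not depend on audiometry. The point concerns the monitoring of participants' hearing.

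**Conclusion.** The point holds. The 500-1600 Hz range contradicts its own description and, followed literally, leaves every threshold above 1.6 kHz unmeasured. It spans 1.68 octaves, against 3.0 to 5.0 for assumed upper limits of 4000 to 16000 Hz. This part is firm, because it needs only the protocol's text. How much harm could be missed depends on the outside assumption that noise damage appears first above about 2-3 kHz.

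The scheduling part is real but softer. The protocol does not secure a battery before the first scan or a known time since the last one. As a result, up to about 4 hours of fMRI may precede the first reading if the first battery follows the fourth scan, and the lag may vary from 0 to about 7 days. The unscanned controls address practice at group level and cannot supply a scanned individual's pre-exposure value.

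**What to change.** - **Audiometry:** correct the upper limit to the high frequency actually intended; if 16000 Hz was meant, write that.
- **Attenuation pilot:** state the frequency range used for the free-field thresholds.
- **First battery:** schedule the first of the existing batteries before the first scan for the 12 scanned participants, and at entry for the 6 controls.
- **Timing:** record the time since the last scan at every battery, so that it can be used when change from the first battery is analysed. A fixed alternation of tests just after and just before scans is one possible design, but it is not needed to repair the text.

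The cost is protocol wording, a few more test frequencies in an existing 20-minute test, one recorded time per battery, and some scheduling effort. No additional battery is required if the first one is simply moved ahead of scanning.

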¹⁶ <https://github.com/poldracklab/fmrip>

al., 2014). A detailed description of the fmripipeline is available online¹⁷.

Standard MEG data cleaning (ICA-based ocular, cardiac and muscle artefact rejection, and exclusion of bad segments/channels) will be followed by data segmentation with respect to events of interest. A MEG-compatible eye-tracker, in combination with EOG traces, will be used to control for unwanted artefacts or synchronizations generated by eye movements (e.g. saccades). MEG data-preprocessing and analyses will be conducted using a combination of open-source tools developed in the [name] lab (NeuroPycon¹⁸, Visbrain¹⁹, Brainpipe²⁰, and TensorPac²¹, as well as well-established freely-available toolboxes, i.e. MNE-python (Gramfort et al., 2013).

Artificial neuronal models

Regarding aim 1, we will develop “vector-quantized variational auto-encoders” (VQ-VAE) that compress the brain images over a time window of 15 seconds, using discrete latent variables (van den Oord et al., 2017). The training of the VQ-VAE will be implemented using all the video and video game fMRI data available for each subject, and a separate model will be trained for each subject. Compressed representation of the video and audio signals, as well as text transcripts of the video will be generated using established techniques (Richard, H, Pinho, AL, Thirion, B, Charpiat, G, 2018). We will then train a sparse attentive backtracking (SAB) recurrent neural network on these discrete latent variable representation to predict future fMRI time series from past time points, using a mixture of past video, audio and functional signals. The performance of the recurrent DNN will be evaluated by the accuracy of prediction of future fMRI time points from past fMRI time points and compared to simple auto-regressive models as a benchmark, using split half cross-validation on available data (half of time points for training, half of time points to evaluate the accuracy of the model).

Regarding aim 2, the same VQ-VAE model trained for aim 1 will be trained to reduce the dimensionality of fMRI time series specifically on the data collected in the language, image, and memory tasks. A separate SAB recurrent DNN will be trained to solve the same task as required for humans. We will evaluate the ability to solve those tasks in isolation, using ten-fold cross validation to evaluate the performance of the models.

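### Aim 1 scores its predictive model on time points that have already trained the VQ-VAE, so the evaluation half is not independent and forecast accuracy may be inflated

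*Protocol*

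**What the plan says.** All of this stands in the protocol section Artificial neuronal models. The SAP was not available.

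**Aim 1, encoder.** The VQ-VAE is to "compress the brain images over a time window of 15 seconds". Its training set is explicit: "The training of the VQ-VAE will be implemented using all the video and video game fMRI data available for each subject". It is fitted within subject: "a separate model will be trained for each subject".

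**Aim 1, predictor and scoring.** A recurrent network is trained "on these discrete latent variable representation to predict future fMRI time series from past time points". The comparator is a plain auto-regressive model. Only the share of data on each side of the evaluation is described: "half of time points for training, half of time points to evaluate the accuracy of the model". Nothing is kept out of the encoder step. Session, run, contiguous block or gap is not mentioned.

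**Aim 2.** The VQ-VAE "will be trained to reduce the dimensionality of fMRI time series specifically on the data collected in the language, image, and memory tasks". A separate recurrent network solves the task and is assessed by ten-fold cross-validation. The unit of a fold is not given, nor whether the encoder is refitted in each fold.

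**Aim 3.** The encoder is the one trained on the movie data. Only the recurrent part is trained on the task, with ten-fold cross-validation within each task. This variant is expected to do better than the Aim 2 networks.

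**The concern.** Cross-validation gives an honest accuracy only if every step that learns from the data is fitted without the evaluation part. In Aim 1 this holds for the second stage but not for the first. The quantity scored is the fMRI series itself, which is also what the auto-encoder was trained to reproduce, so this is not harmless pre-processing on an unrelated input.

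The Aim 1 hypothesis in Summary and objectives, that large networks can reproduce brain dynamics accurately, is judged on this accuracy and on its margin over the auto-regressive benchmark. That benchmark, as described, has no stage that has seen the evaluation half. A gain by the network could therefore be partly genuine and partly carried by the encoder, and the planned analysis could not separate the two.

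The loosely worded split is a second, conditional problem. If single time points were allotted at random, training and test points would lie side by side within the same 15-second window.

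**Working it through.** **1. What can be reproduced.** The protocol gives no expected accuracy, effect size or sampling interval. Its only derived design figure is the core cohort, 3 tasks × 4 participants = 12. It reproduces and plays no part here.

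**2. Overlap as written (Aim 1).** With N time points per subject, the encoder uses N and the evaluation half is 0.5N, all inside N. The share of the evaluation half seen by the encoder is 0.5N / 0.5N = 100%. Fitting the encoder on the training half makes it 0%.

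**3. Can this reach a forecast, not just a reconstruction?** Two illustrative simulations used first-order autoregressive signals, a k-means codebook in place of the VQ-VAE, and ridge forecasting scored against the simulated measurements. None of these settings comes from the protocol.

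*(a)* 100 channels, 2000 points, 256 codes, contiguous halves, one step ahead, 4 replicates. Entries are held-out R².

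| Autocorrelation | Codebook on all data | Codebook on training half | Difference | AR benchmark |
|---|---|---|---|---|
| 0.5 | 0.06 | −0.04 | 0.10 | 0.25 |
| 0.8 | 0.43 | −0.22 | 0.65 | 0.64 |
| 0.9 | 0.62 | −0.26 | 0.88 | 0.81 |

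On white noise the all-data codebook gave a forecast R² of −0.06, against 0.00 for the AR benchmark.

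*(b)* Session split, non-overlapping 10-point windows. Entries are R² with the codebook on all data versus training sessions only.

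| Autocorrelation | 32 codes | 128 codes | 256 codes |
|---|---|---|---|
| 0.8 | 0.00 vs 0.00 | 0.04 vs −0.04 | 0.15 vs −0.10 |
| 0.9 | 0.08 vs 0.04 | 0.20 vs 0.03 | 0.34 vs −0.05 |

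The leak can raise forecast accuracy even with a clean session split. It needs autocorrelation and grows with the size of the codebook.

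**4. Split unit, only if time points are drawn at random.** The chance that an evaluation point has at least one training point in its preceding 15-second window is 1 − 0.5^k, with k whole samples in 15 s. The sampling interval is assumed:

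- 2.0 s: k = 7, 1 − 0.5^7 = 99.2%
- 1.5 s: k = 10, 1 − 0.5^10 = 99.9%
- 1.0 s: k = 15, 1 − 0.5^15 = 99.997%

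The effect on a flexible learner was illustrated with 5-nearest-neighbour forecasting and no encoder (20 channels, 10 sessions × 300 points, 10-point windows, 4 replicates). The best attainable R² at h steps is φ^(2h), where φ is the autocorrelation.

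| φ, steps ahead | Best attainable | Learner, random points | Learner, sessions | AR, either split |
|---|---|---|---|---|
| 0.8, 5 | 0.8^10 = 0.11 | 0.43 | −0.39 | 0.11 |
| 0.9, 5 | 0.9^10 = 0.35 | 0.70 | −0.42 | 0.34–0.35 |
| 0.8, 1 | 0.8^2 = 0.64 | 0.48 | −0.13 | 0.64 |

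At five steps under random points, the learner scores above what is attainable, while the AR benchmark does not move. At one step it is inflated but stays below AR.

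**5. Aims 2 and 3 side by side.** The Aim 3 encoder learns from movies and is scored on task data, so its task folds did not train it. The Aim 2 encoder learns from task data and is scored on task data. Whether the scored fold is excluded is not stated.

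**The case against.** Several points on the other side have force.

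- **The split may be sound.** "half of time points for training, half of time points to evaluate the accuracy of the model" gives a proportion, not an allocation. First half against second half, or grouping by session, also fits, and forecasting future from past points to contiguous series. This stands. A reader might infer that the protocol splits by scattered time points, but the text does not say so, and the figures in step 4 of the working are conditional.
- **No false win has been shown for the encoder leak.** A reader might infer that the network would beat the benchmark even with no signal. The simulations do not support that: on white noise the leaked forecast was no better than AR, and in simulation (a) it stayed below AR at every autocorrelation. A codebook fitted on all of a pure-noise series does appear to explain 23% of held-out variance against 2%, but that is reconstruction of the same point, whereas Aim 1 scores prediction of later points.
- **Aim 2 may be clean.** It does not say that all task data train the encoder or that this happens outside the folds, and the encoder step is dimension reduction without task labels. It is tempting to say that Aim 2 repeats the fault. That is a possible reading, not a stated fact. If it did leak, the bias would run against the Aim 3 hypothesis, so it could not create a false finding of transfer.
- **The SAP may give detail.** That covers fold-wise refitting in Aim 2. It does not cover Aim 1, where the protocol itself fixes the encoder's training set, the evaluation share and the comparator.

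None of this removes the 100% overlap in Aim 1.

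**Conclusion.** The point holds for Aim 1 as written and should be corrected. The evaluation half is wholly contained in the encoder's training data, and the comparison with the auto-regressive benchmark is uneven. The expected direction is upward for the network's forecast accuracy, given that fMRI is autocorrelated.

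The size is unknown. It depends on the autocorrelation, sampling interval, forecast horizon and encoder capacity, none of which the protocol gives in usable form. The simulated differences run from 0.00 to 0.88 in R² across the settings tried, which shows a mechanism and is not an estimate for this study.

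The split unit in Aim 1 is an ambiguity to close. Encoder refitting and fold unit in Aim 2 are points to clarify. Aim 3 is not exposed to the encoder leak.

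**What to change.** **Aim 1.** State that every learned stage (VQ-VAE, recurrent network and any tuning) is fitted on the training half only. Define the halves by whole sessions, so that no 15-second window crosses the split. The Overview of the project foresees roughly 50 fMRI sessions per subject, so about 25 / 25 is feasible. Score the network and the auto-regressive benchmark on the same held-out sessions.

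**Aim 2.** State that the VQ-VAE is refitted within each training fold and that folds are grouped by session or run.

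**Aim 3.** The movie-trained encoder can stay as it is.

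**Cost.** Protocol wording and compute: if both halves take a turn as test set, two encoder fits per subject in Aim 1 instead of one, and up to ten per cross-validation in Aim 2. The encoder learns from about half the data when it is being evaluated, and reported accuracy will probably be lower. No extra scanning is needed.
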